January 26, 2024

Title: Creatine Supplementation At Simulated Altitude

Project Personnel: [name]. Department of Kinesiology and Public Health [contact]; [name]

Purpose

Military personnel are frequently exposed to extreme environments, including high altitude and hypoxic conditions, which severely limit exercise capacity and performance. For example, over 775,000 soldiers have been deployed to Afghanistan since 2001, many of which have been exposed to potentially life-threatening elevations above 4000 meters (13,123 ft) in locations such as the Tora Bora mountains (1,2). Surprisingly, very few methods have been developed to mitigate the effects of hypoxia on exercise performance (3), despite the Department of Defense prioritizing this area of research.

Previous studies have shown that creatine supplementation increases exercise performance at sea-level (4,5). Our team showed a 4% improvement in exercise performance with creatine supplementation (vs. Placebo) (4). However, no published study has examined whether creatine supplementation increases performance at altitude. The purpose of this study is to determine the effects of creatine supplementation on exercise performance at simulatedaltitude.

Methods and Protocol

Subjects

Sixty healthy adults (30 men and 30 women) will be recruited and enrolled. Inclusion criteria includes: 1) 18-40 years old, 2) BMI 18.5-40.0 kg/m² 3) habitually active (>150 minutes per/wk of moderate-vigorous physical activity). Exclusion criteria includes: 1) pregnant or trying to become pregnant 2) recent use of creatine supplementation and 3) supplement allergies.

Subject Recruitment & Study location

Recruitment efforts will be focused on California Polytechnic State University and the surrounding area. Participants will be recruited via flyers hat will be posted in physical locations around campus and the San Luis Obispo, CA area. These flyers will also be distributed electronically via campus lists and classes, and appropriate social media outlets. The flyer contains a QR code that can be used to access a contact information survey and preliminary eligiblity (See eligiblity script). If the participant is deemed eligible for the study, they will be asked to schedule a Zoom or in-person meeting with a member of the research staff to go over the study protocol in more detail and address any questions or concerns the participant may have.

If the participant is interested in taking part in the study, they will be provided with an informed consent form (electronic via Adobe Sign or paper copy). Subjects will give both verbal and written informed consent. Similar to our previous studies, subjects may sign the informed consent with ink signature or via electronic signature using RedCap. RedCap is a secure web application for building and managing online surveys and databases. All testing and procedures will occur in the Human Performance Laboratory in the Kinesiology building (43A) at California Polytechnic State University.

Preliminary testing

Body weight via digital scale and height via stadiometer will be obtained. Subjects will also complete a physical activity questionnaire, health history questionnaire, and demographics questionnaire. Subjects will then complete a familiarization exercise performance test (repeated sprint test). Previous studies have shown a learning curve with the repeated sprint test (subjects get better at the test), and therefore will complete a familiarization test. The repeated sprint test involves six, 10-second sprints on a cycle ergometer (Racer-Mate Inc, Seattle, WA, USA) with 60 second recovery between each sprint [6]. Following a brief self-selected warm-up, the subject will build to their maximal cadence and then pedal maximally against a resistance of 0.075 kg/kg body weight for 10 seconds, followed by 60-seconds of recovery. The test will take approximately 10-15 minutes total time. We have previously used a similar protocol after creatine supplementation at sea-level (4), and the test is a validated measure of high-intensity exercise performance that mimics many physiological demands of military performance (6-8). Outcomes measures are peak power (watts), relative peak power (watts per kilogram), and fatigue index (watts per second).

Baseline Testing

At least 24 hours after the familiarization repeated sprint test, subjects will then return to the laboratory after an overnight fast. Subjects will complete a baseline Acute Mountain Sickness score (Lake Louise AMS score). Participants will then complete a baseline repeated sprint test, as described above. During the test, oxygen saturation and pulse will be collected on the index finger using a non-invasive pulse oximeter (ZacVrate, Inc.).

Randomization and Supplementation

After baseline testing, subjects will be randomized (by sex, age, ethnicity, and peak power), using a double-blinded parallel design, to placebo (calcium 500 mg) or creatine supplementation (20 grams) for 2 days. The supplements will be given to subjects in equal numbers of unidentifiable capsules. As we previusly described (4), each total daily dose will be divided into 4 capsules to reduce gastrointestional stress. Subjects will be instructed to take 4 capsules a day, several hours apart, for two days straight (4,9,12,13).

Simulated Altitude Testing After the 2 day supplementation treatment, subjects will arrive in the laboratory after an overnight fast and weight will be obtained. Subjects will rest for 30 minutes breathing a hypoxic gas mixture containing 12.8% oxygen, equivalent to 4000 meters elevation (13,123 feet elevation). The hypoxic gas will be emitted from a hypoxic generator (Hypoxico Hypoxic Generator, New York, NY) that lowers the oxygen content of room air and administers it to subjects through a HEPA filter and sealed facemask. This is a validated method commonly used to simulate altitude in research (10). Subjects will then complete the Acute Mountain Sickness score, and then perform the same repeated sprint test as described above. Oxygen saturation and pulse will be collected on the index finger using a non-invasive pulse oximeter (ZacVrate, Inc.).

After completion of the study, a researcher will go over the subjects' repeated exercise test results with them in person.

Description of Risks and Benefits

General Risk of Exercise Despite the well-documented benefits, there are minimal risks associated with exercise (11). Participants may experience fatigue and muscle soreness due to an increase in physical activity from previous sedentary states. These health risks are small in people with no prior history of cardiovascular, respiratory, or musculoskeletal disease or injury. Any ordinary fatigue or muscle soreness is temporary and usually lasts 24-96 hours (about 4 days). With any exercise, there is a slightly increased risk of acute cardiovascular complications. The American College of Sports Medicine notes that although the relative risk of unfavorable outcomes slightly increases with exercise, the absolute risk of a cardiac event is still very low (1 per 133,000 men and 1 per 769,000 women). To ensure the safety of subjects during all exercise tests, we will follow American College of Sports Medicine guidelines. During the test, if the subject experiences any problems (light-headed, nauseous, excessive redness in the face, or heart palpitations) the exercise test will be immediately stopped. Additionally, we will be monitoring the participant's oxygen saturation and provide additional caution if their oxygen saturation levels drop below 80% (which is not expected). After the exercise test, subjects will cool-down for a 3-minute period or until heart rate reaches close to resting values. There will always be at least 2 CPR certified persons in the room during testing, one who can perform CPR and one who can call 911. The lead investigator and/or trained students have administered numerous exercise tests with no adverse events.

Supplementation Risks

Creatine supplementation has minimal side effects, espically short-term supplementation. There is a slight risk of acute water retention [7]. Creatine supplementation has been deemed safe in the dosages prescribed in this study in individuals free of gastrointestinal, metabolic, renal, liver, or cardiorespiratory diseases [8,9]. Individuals with these conditions will be screened and excluded from participation using the previously described screening methods.

Simulated-Altitude

There are minimal risk associated with simulated altitude for 45 minutes. Subjects may transiently feel lightheaded, dizzy, or fatigued, and may stop at any time.

Questionnaires

Subjects may omit any questions on the surveys (physical activity, health history, demographics, Acute Mountain Sickness score).

Benefits

There are no direct benefits for participating in this study, and subjects will not be compensated.

Data Collection

Statistics and Sample-size Calculation A repeated measures ANOVA will be used to determine differences on all variables of the repeated sprint test, adjusting for age, sex, ethnicity, and peak power A $\alpha < 0.05$ will be considered significant, and Tukey's HSD tests will be used to correct for multiple comparisons.

Data Storage, Sharing, and Destruction All data will be collected by trained student researchers under the authorization of the lead investigators. Data will be examined in a confidential fashion to preserve the privacy of each participant. All members of the research staff will have completed the required CITI and Cal Poly training modules. The data collected in this study will be accessible only to the researchers involved. All data will be stored on a password-protected computer and transferred to a password-protected cloud-based storage drive. All data will be de-identified using both a unique study and participant ID. The file linking the participant's identifiable information to their ID number and confidential data will be kept in a separate password-protected location. After 7 years following the completion of the study, hard copies of the data will be destroyed. Data specific to the aim of this study will be shared with scientific journals for publication purposes only, when appropriate.

Works Cited

- 5. Kreider RB. Effects of creatine supplementation on performance and training adaptations. *Mol Cell Biochem*. 2003;244(1):89-94. doi:10.1023/A:1022465203458
- 6. Bar-Or O. The Wingate anaerobic test an update on methodology, reliability and validity. *Sport Med.* 1987;4(6):381-394.

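### The warm-up before each sprint test is left to the subject and nothing keeps it the same at baseline and at altitude: a small, avoidable source of within-subject noise

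*Protocol*

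**What the plan says.** The Preliminary testing section of the Protocol describes the repeated sprint test once. It fixes the number of sprints (six), their length (10 seconds), the recovery (60 seconds) and the resistance (0.075 kg per kg body weight). The lead-in is not fixed: "Following a brief self-selected warm-up, the subject will build to their maximal cadence and then pedal maximally". No duration, load or cadence is given for the warm-up.

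The later tests borrow this description. Under Baseline Testing: "Participants will then complete a baseline repeated sprint test, as described above". Under Simulated Altitude Testing, subjects "perform the same repeated sprint test as described above".

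The results read from the test are listed under Preliminary testing: "Outcomes measures are peak power (watts), relative peak power (watts per kilogram), and fatigue index (watts per second". Peak power is also a randomization factor (Randomization and Supplementation) and an adjustment variable (Statistics and Sample-size Calculation).

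The same section gives the reason for a familiarization test: "Previous studies have shown a learning curve with the repeated sprint test (subjects get better at the test". The only effect size in the document is in the Purpose section: "Our team showed a 4% improvement in exercise performance with creatine supplementation (vs. Placebo".

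**The concern.** The phrase about performing the same test could be taken to standardize the warm-up. It does not: the test being repeated leaves the warm-up to the subject, so what is repeated is the freedom to choose, not the warm-up that was chosen. A subject may do a longer or harder warm-up on one day than on the other and still follow the protocol.

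The protocol otherwise works to make the two tests comparable. Sprint length, recovery and relative resistance are fixed, both tests follow an overnight fast, and a familiarization test is added because of learning. The warm-up is a simpler source of variation left open. At stake is precision: any part of a subject's sprint result that depends on that day's warm-up enters the change from baseline as error, in a trial of 60 people where the only cited effect is 4%.

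**Working it through.** **1. How much room the protocol leaves.** The Protocol puts the whole test at approximately 10 to 15 minutes.
- Sprints: 6 × 10 s = 60 s.
- Recoveries: 5 × 60 s = 300 s, or 6 × 60 s = 360 s if one follows the last sprint.
- Fixed part: 360 to 420 s, that is 6 to 7 minutes.
- Remainder: from 10 − 7 = 3 to 15 − 6 = 9 minutes.

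The remainder covers warm-up, build-up to maximal cadence and any set-up. The warm-up is thus bounded but not fixed. This is an inference from approximate figures.

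**2. The plan's own sample size.** The Protocol says: "Sixty healthy adults (30 men and 30 women) will be recruited and enrolled". It states no SD, power or target difference, so 60 cannot be reproduced. What follows is an illustration, not a check of a stated figure.

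**3. Inputs.**
- Effect: 4% (Purpose; stated for exercise performance at sea level).
- Arms: 30 each (1:1 assumed; the ratio is not stated).
- Alpha: 0.05 (Protocol), taken as two-sided (assumed).
- SD0, the SD of the change from baseline without warm-up noise: 5% or 6% of baseline (assumed).
- w, the visit-to-visit SD that warm-up adds to one test: 1% or 2% (assumed). A subject's stable habit cancels in the change; only variation between visits counts.

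**4. Formulas.** With independent noise at both tests, SD = √(SD0² + 2w²). By the normal approximation, power = Φ(4 / (SD × √(2/30)) − 1.96), and n per arm for 80% power = 2 × (1.96 + 0.84)² × SD² / 4², rounded up.

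Worked example, SD0 = 5 and w = 2: SD = √(25 + 8) = 5.74; 4 / (5.74 × 0.258) = 2.70; 2.70 − 1.96 = 0.74; power = 0.77.

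| SD0 | w | SD of change | Power, 30 per arm | Loss (points) | n per arm for 80% |
|---|---|---|---|---|---|
| 5% | 0 | 5.00% | 0.873 | – | 25 |
| 5% | 1% | 5.20% | 0.846 | 2.7 | 27 |
| 5% | 2% | 5.74% | 0.769 | 10.4 | 33 |
| 6% | 0 | 6.00% | 0.733 | – | 36 |
| 6% | 1% | 6.16% | 0.710 | 2.3 | 38 |
| 6% | 2% | 6.63% | 0.646 | 8.7 | 44 |

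**5. Sensitivity.** If SD0 runs from 4% to 8%, w = 1% costs 1.2 to 2.7 points and w = 2% costs 4.4 to 10.4. At w = 0.5% the loss is below 1 point throughout.

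**The case against.** The strongest reply is that this is a deliberate choice and contradicts nothing. A self-selected warm-up need not differ between visits; familiarization gives subjects a chance to settle on a routine; and the warm-up is described as brief within a bounded test time. All of that stands, and it is why the point is minor. But consistency then rests on habit, and nothing in the Protocol requires it.

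It can also be said that every noise figure is assumed. That stands too. The documents do not show that warm-up affects these outcomes, still less by how much. An SD0 taken from tests with self-selected warm-ups would already contain the noise, so adding w would count it twice. The illustration uses change scores without the planned covariate adjustment, and the 4% is not specifically peak power and not at altitude.

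Three stronger readings are tempting and not supported:
- **Bias between arms.** The design is parallel and double-blind, with randomization after baseline. A shift in warm-up under hypoxia is expected equally in both arms. It could blur the sea-level-to-altitude contrast, but that is not the stated purpose and already mixes altitude with time and repeat testing.
- **Subjects would warm up less on 12.8% oxygen.** Nothing in the Protocol says so.
- **Peak power comes from the first sprint, where warm-up would matter most.** The Protocol does not say which sprint yields it.

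Nor should the triple use of peak power be pressed. Noise in it as a randomization factor only slightly loosens balance, and as a covariate only slightly reduces the gain in precision. The outcome is where it counts.

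**Conclusion.** The point holds as a cheap improvement. The Protocol leaves the warm-up to the subject at every test and nothing keeps it the same at baseline and altitude. The expected consequence is extra within-subject noise in the sprint outcomes; the comparison of creatine with placebo remains valid.

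The size is unknown. On the assumptions shown, 1% per-test noise costs about 2 to 3 points of power and 2% about 9 to 10. These figures show what kind of loss is possible; they are not an estimate for this trial. The defect in the text can be verified, but its practical weight cannot, and it may be small.

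**What to change.** In Preliminary testing, replace the self-selected warm-up with one of two rules:

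1. Record the duration and load of each subject's warm-up at familiarization, and reproduce both at the baseline and altitude tests. This keeps individual preference and removes drift between visits.
2. Set one light warm-up, of stated duration and load, for all subjects at all tests.

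Either takes one sentence in the protocol and one line on the test sheet, with no extra visit, staff or equipment. The downside is slightly less freedom for the subject on the day. If a subject departs from the recorded warm-up, note it on the sheet.

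### Do 20 g of creatine and four capsules a day conflict, and is the blind left unsupported?

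*Protocol*

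**What the plan says.** All the relevant statements stand in one paragraph of the Protocol, Randomization and Supplementation.

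- Allocation is made "using a double-blinded parallel design", to "placebo (calcium 500 mg) or creatine supplementation (20 grams) for 2 days".
- On presentation: "The supplements will be given to subjects in equal numbers of unidentifiable capsules".
- On division: "each total daily dose will be divided into 4 capsules". The reason given is gastrointestinal tolerance, and the team's earlier study (reference 4) is cited for the method.
- The instruction to subjects: "Subjects will be instructed to take 4 capsules a day, several hours apart, for two days straight".

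Two other places bear on the point. Supplementation Risks states: "Creatine supplementation has been deemed safe in the dosages prescribed in this study". Preliminary testing describes an effort-dependent test, in which subjects "pedal maximally against a resistance of 0.075 kg/kg body weight for 10 seconds", and says the team has used a similar test after creatine at sea level, again citing reference 4.

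The Protocol does not label 20 g or 500 mg as per day. It does not give the content of one capsule, its size, its filled weight or any filler.

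**The concern.** Two things look wrong.

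The first is the creatine amount. Dividing it by the capsule count gives several grams per capsule, which is more than one expects a swallowable capsule to hold. If someone dispensed four ordinary capsules a day because the text says four, subjects could receive much less than the stated amount. The trial would then test a weaker intervention than it describes, and the safety statement, which refers to the dosages of this study, would rest on an unclear quantity.

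The second is the blind. The stated contents of the two arms are far apart, and the Protocol does not say how the capsules are made alike. The sprint outcomes depend on maximal effort, so a subject or tester who guessed the allocation could shift the result. If the filled weights differed, anyone handling both products might tell them apart.

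**Working it through.** **Inputs from the Protocol (Randomization and Supplementation):** creatine 20 g; calcium 500 mg; 4 capsules per daily dose; 4 capsules a day for 2 days. The Protocol states no content per capsule, so there is no such figure to reproduce.

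**Step 1. Do the stated figures agree?**

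Content per capsule = daily amount / capsules per day.

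- 20 g as the daily amount: 20 / 4 = 5 g per capsule. Back-check: 4 x 5 g = 20 g a day, and 8 x 5 g = 40 g over two days.
- 20 g as the two-day total: 20 / 2 = 10 g a day, and 10 / 4 = 2.5 g per capsule. Back-check: 8 x 2.5 g = 20 g.

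Either way the numbers multiply out. The daily reading is the natural one, because the paragraph goes on to speak of each total daily dose.

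**Step 2. Where does the misfit come from?**

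It needs a capsule capacity, which the Protocol does not give. The range below is an assumption, 0.5 to 2.0 g. Capsules needed = daily amount / capacity, rounded up.

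| Assumed capacity (g) | Held by 4 capsules (g) | Share of 20 g | Capsules for 20 g | Capsules for 10 g |
|---|---|---|---|---|
| 0.5 | 2 | 10% | 40 | 20 |
| 1.0 | 4 | 20% | 20 | 10 |
| 1.5 | 6 | 30% | 14 | 7 |
| 2.0 | 8 | 40% | 10 | 5 |

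At no capacity in this range do four capsules hold the stated amount, on either reading. So if capsules are of this size, four cannot be a literal capsule count. That conclusion comes from the assumption and not from any disagreement between two statements in the Protocol.

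**Step 3. Is there a reading that removes it?**

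Yes. If four counts divided servings, each serving is 20 / 4 = 5 g, made up of as many capsules as needed. At 0.5, 1.0, 1.5 and 2.0 g that is 10, 5, 4 and 3 capsules per serving, or 40, 20, 16 and 12 a day. The surrounding text supports this reading: the purpose of dividing is tolerance, the intakes are spaced through the day, and the method is said to follow an earlier study by the same team.

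**Step 4. What do the contents say about the blind?**

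- Calcium per capsule, 500 mg as a daily amount: 500 / 4 = 125 mg. Ratio to creatine: 5000 / 125 = 40.
- Calcium as a two-day total: 250 / 4 = 62.5 mg. Ratio to 5 g: 5000 / 62.5 = 80.
- Calcium as 500 mg per capsule: the ratio to 2.5 g is 2500 / 500 = 5.

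The ratio runs from 5 to 80 across the readings. It compares stated active content only. It says nothing about filled weight, because filler is neither described nor ruled out. The features the Protocol does fix are equal capsule numbers and capsules that cannot be identified.

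**The case for a change.** The strongest case for a change is that the amount taken defines the intervention, and a protocol should be executable as written. Capsules are mentioned both in the division of the dose and in the instruction to subjects, so the word is not a single slip. If four means servings, the number of capsules per serving is missing. A literal reader and a reader who starts from 20 g would dispense different quantities: on the assumed capacities, 2 to 8 g against 20 g a day. The earlier study may supply the detail, but it is not at hand, and product content is not something a statistical analysis plan would add. Clarifying it would cost a sentence or two.

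Part of this stands. The per-day label, the unit that four refers to and the content per capsule are not written down. The divergence, however, requires someone to prepare four small capsules a day while knowing that the stated amount is 20 g. A team filling the capsules to a stated amount, by a method it says it has described before, would meet that mismatch when preparing the product and resolve it there.

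The safety argument carries little weight. On the capacity assumption that creates the problem, literal adherence gives less than the stated amount, so the sentence in Supplementation Risks is not shown to be wrong in an unsafe direction.

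The blinding argument is weaker still. It infers visible or tangible differences from active content alone. In a parallel design each subject receives one product and has no second one to compare. The Protocol does not say that the people who dispense also run the sprint tests, so the route through staff is conjecture.

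**Conclusion.** No change is called for. The quantities in the Protocol are consistent: 5 g per capsule on the daily reading, 2.5 g on the less likely two-day-total reading, and both return the stated amount. The apparent shortfall, with four capsules holding 10% to 40% of 20 g, depends wholly on an assumed capacity of 0.5 to 2.0 g that is not in the document. The likeliest explanation is loose wording for four divided servings.

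The blind is briefly described but not contradicted. Double-blind allocation, equal numbers and unidentifiable capsules are all specified, and how size and filled weight are matched is a manufacturing detail that a short protocol may leave out. Its absence does not show that the blind fails.

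The analysis does not turn on the point either. The repeated measures ANOVA compares randomized arms, and content per capsule does not enter it. This judgement assumes that the product is prepared to the stated amount and that the capsules are made alike as the Protocol requires. It takes no position on which dose or schedule is right.

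### The only saturation trigger (80%) is called unexpected without support and has no defined response; at 12.8% oxygen, lower readings should be treated as possible

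*Protocol*

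**What the plan says.** The saturation trigger is in the Protocol, Description of Risks and Benefits, General Risk of Exercise: staff will "provide additional caution if their oxygen saturation levels drop below 80% (which is not expected". The sentence follows text about all exercise tests and does not separate room air from hypoxia. For a listed symptom (light-headedness, nausea, facial redness, palpitations) the same paragraph is definite: "the exercise test will be immediately stopped".

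The exposure is described under Simulated Altitude Testing: "Subjects will rest for 30 minutes breathing a hypoxic gas mixture containing 12.8% oxygen, equivalent to 4000 meters elevation". After that, "Subjects will then complete the Acute Mountain Sickness score, and then perform the same repeated sprint test as described above". Preliminary testing gives the test length: "The test will take approximately 10-15 minutes total time". The Simulated-Altitude risk paragraph reads "There are minimal risk associated with simulated altitude for 45 minutes" and "Subjects may transiently feel lightheaded, dizzy, or fatigued, and may stop at any time"; it names no saturation level. Enrolment is planned as follows: "Sixty healthy adults (30 men and 30 women) will be recruited and enrolled".

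**The concern.** Two things are joined in one sentence. The first is a prediction, that saturation will stay at or above 80%, with no predicted value, pilot result or citation behind it. Reference 10 is cited for the method of producing hypoxia, not for the saturation to expect. The second is a response that has no content: nothing says whether to repeat the reading, pause, remove the mask or stop.

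The explicit stop depends on symptoms. A subject who reads below 80% and feels well falls between the two rules. Staff who have been told the reading is not expected may take it for artefact or improvise, and the ethics board has been given a more favourable picture than the stated gas supports. What is at stake is subject safety and the accuracy of the risk statement. The sprint outcomes and their analysis are not in question.

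**Working it through.** **1. Does the trigger apply under hypoxia?** The protocol does not say outright that the mask stays on for the sprints, but the times imply it: 30 minutes of rest plus a test of 10 to 15 minutes gives 40 to 45 minutes, and the risk section states 45. The familiarization and baseline tests are not described as hypoxic.

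**2. The plan's own figure.** There are no inputs behind the 80% expectation, so it cannot be reproduced. The related figure can: with an assumed standard-atmosphere pressure of about 462 mmHg at 4000 m, 20.93% × 462/760 = 12.7%, in line with the stated 12.8%.

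**3. Formulas.**
- Inspired PO2 = 0.128 × (PB − 47). At an assumed sea-level PB of 760 mmHg this is 0.128 × 713 = 91.3 mmHg.
- Alveolar PO2 = inspired PO2 − PaCO2 × (0.128 + 0.872/R).
- Arterial PO2 = alveolar PO2 − A-a gradient.
- P = arterial PO2 × 10^(0.48 × (pH − 7.40)), with resting pH = 7.40 + 0.008 × (40 − PaCO2).
- Saturation (Severinghaus) = 100/(23400/(P³ + 150P) + 1).

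Every input except 12.8% is an assumption. Room-air check (20.93% oxygen, PaCO2 40, R 0.80, A-a 8, pH 7.40): 97.2%, as it should be.

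**4. One case at rest.** PaCO2 36, R 0.85, A-a 8: alveolar PO2 = 91.26 − 36 × (0.128 + 0.872/0.85) = 49.7; arterial PO2 = 41.7; pH = 7.432; P = 43.2; saturation = 78.9%. With PaCO2 34 and A-a 6 instead, saturation is 83.9%.

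**5. Where 80% is crossed at rest (R 0.85).**

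| PaCO2 | Alveolar PO2 | Arterial PO2 at 80% | A-a gradient at crossing |
|---|---|---|---|
| 34 | 52.0 | 42.0 | 10.0 |
| 36 | 49.7 | 42.8 | 7.0 |
| 38 | 47.4 | 43.5 | 3.9 |

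(Gradients are from unrounded values.) At PaCO2 32 and R 1.0 the gradient would have to reach 18.0, outside the assumed range.

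**6. Resting grid.** PaCO2 32–38 (step 1), R 0.80–1.00 (step 0.05), A-a 3–10 (step 1): 7 × 5 × 8 = 280 cells.

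| PB (mmHg) | 5th–95th percentile of cells | Cells below 80% |
|---|---|---|
| 750 | 73.5–88.0% | 30% |
| 760 | 75.3–88.8% | 21% (60 of 280) |
| 765 | 76.1–89.1% | 18% |

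The median at 760 mmHg is 83.7%.

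**7. Narrower resting box.** PaCO2 32–35, R 0.85–1.00, A-a 3–8: 4 × 4 × 6 = 96 cells, none below 80%; the minimum is 80.5%, at PaCO2 35, R 0.85, A-a 8.

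**8. Sprint check.** PaCO2 26–34, R 0.95–1.15, A-a 8–20 (step 2), pH 7.25–7.40: 1260 cells, median 80.2%, 616 (49%) below 80%. The share runs from 8% at A-a 8 to 91% at A-a 20. The model is steady-state and the sprints last 10 seconds, so this shows only that 80% lies inside the range.

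**9. Without the pH shift.** At rest with R 0.85: 86.1% (PaCO2 30, A-a 5), 81.6% (35, 5), 80.0% (32, 10), 76.1% (35, 10). The range still spans 80%.

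**10. Benchmark, not an estimate.** With 60 independent subjects, seeing no reading below 80% is the likelier result only if the chance per subject is at most 1 − 0.5^(1/60) = 0.0115, about 1.1%.

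**The case against.** The strongest reply is that the expectation is not contradicted. The modelled resting median is above 80%, and 220 of 280 cells (79%) are at or above it. Not expecting something differs from calling it impossible, and the same sentence provides for monitoring and a reaction. The low tail comes from pairing high PaCO2, low R and a large gradient (38, 0.80 and 10 give 68.3%), and the narrower box removes it. All of this stands. It rules out calling 80% an ordinary resting value, or the expectation disproved. It does not supply the missing support, because the narrower box is assumed too and clears the threshold by only half a point.

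Existing safeguards also count: the symptom stop, ACSM guidelines, two CPR-certified people in the room, the right to stop, and exclusion of cardiorespiratory disease. They limit the harm, but none of them sets a response for a symptom-free low reading.

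A reader might go further in three ways that the documents do not support:
- **A count of affected subjects.** Grid cells are not people. Assumed means of 84–86% with SDs of 3–5 points would put roughly 1 to 13 of 60 below 80%, but a mean of 88% with SD 3 leaves only a 21% chance of any. The protocol gives neither a mean nor an SD.
- **Sprints as the more dangerous phase.** That depends on assumed acidosis and gradient. At pH 7.40 the sprint median is 83.8%, practically the resting value.
- **Subjects misinformed about desaturation.** The consent pages are not available, so this cannot be judged.

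**Conclusion.** The point holds as a minor safety correction for the hypoxic session. The firmer half needs no model: the one saturation trigger leads to no defined action for a subject without symptoms. The other half is conditional: under assumed PaCO2, R, gradient, pH and barometric pressure, 80% falls within the plausible range at rest and in the sprints, though narrower plausible resting inputs stay just above it. Readings below 80% should be planned for as possible, with no frequency attached. The expectation is reasonable for the room-air tests. Alpha, power and sample size are unaffected.

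**What to change.** Amend one sentence of General Risk of Exercise in two places.

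1. Replace the parenthesis with: *not expected on room air, but possible while breathing 12.8% oxygen*.
2. Replace the undefined caution with a graded response. Below 80%, repeat the reading with the hand still and check for symptoms before the next sprint. Remove the mask and stop if symptoms appear, if saturation stays below a lower limit, or if it stays low for a set duration. The investigator and ethics board fix that limit and duration in advance.

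Keep the symptom-based stop. Do not write the modelled ranges into the protocol. Do not make 80% an automatic stop: a level that may be crossed at this oxygen fraction could then cut short the only post-treatment sprint test.

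The device, staff and visits stay the same. The cost is a short amendment, a slightly less favourable risk statement, and some interrupted or incomplete post-treatment tests, which should be recorded with the reason for stopping.
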